5.5 Duration of Study Participation

Both psychiatrists and patients will be participants for 6 months duration.

5.6 Total Number of Participants and Sites

Study subjects are not NYULH employees or patients. In total, this study plans to include 420 participants:

- A. Psychiatrists (n=20)
- B. Patient Cohort (n=400 smokers)

Participants will be recruited from the VA NY Harbor Healthcare System, at the Manhattan and Brooklyn campuses.

Recruitment will end when approximately 20 psychiatrists and 400 smokers are enrolled.

No recruitment or consenting will take place at NYULH.

5.6.1 Reasons for Withdrawal or Termination

Participants are free to withdraw from participation in the study at any time upon request. An investigator may terminate participation in the study if:

- Any clinical adverse event (AE), laboratory abnormality, or other medical condition or situation occurs such that continued participation in the study would not be in the best interest of the participant
- The participant meets an exclusion criterion (either newly developed or not previously recognized) that precludes further study participation

CONFIDENTIAL

5.6.2 Handling of Participant Withdrawals or Termination

After a participant withdraws, the study will not conduct any additional follow-up with the participant. Participants who withdraw will not be replaced.

6 Behavioral/Social Intervention

6.1 All Participants

Both Arms: Psychiatrist Training and Academic Detailing

Since psychiatrists cite lack of training as barrier to providing smoking cessation treatment, both arms will receive a 1-hour training in helping their patients quit smoking. One hour was chosen based on the provider trainings held by [name] (MPI), and to maximize feasibility and fidelity (e.g., psychiatrist attendance) of the training. We will provide this education to both study arms, because education alone is necessary but not sufficient to change provider behavior.[25]

The training will be a mix of content education and process education (Table 1). Our approach will be adapted from the one [name] used to train primary care and mental health providers about depression[26] and the *Psychiatry Rx for Change* training program

Table 1: Psychiatrist training

Content Education	
• Epidemiology of tobacco use in psychiatric patients• Tobacco treatment guidelines• Linking cessation to mental health treatment norms and outcomes• Common myths about smoking in mental health patients• 3A's model – ask, advise, assist• Pharmacological Aids (focus on PHS guidelines)• Counseling Strategies• Overview of local cessation program• Medication Interactions with smoking• Patient resistance (motivational interviewing demonstration)
Process Education	
• How to use clinical reminder, order NRT and refer

for psychiatry residents.[27] The lecture will include a 15-minute demonstration of motivational interviewing[28] (MI) in order to help psychiatrists provide brief motivational enhancement for patients resistant to treatment[29] (identified as a barrier in our prior psychiatrist interviews).

To reinforce provider self-efficacy in treating mental health patients for smoking, we will also implement academic detailing (educational outreach) for providers in both arms. Academic detailing has consistently shown improvements in provider behavior.[30] Two study investigators will make a brief outreach visit to each psychiatrist, at least one of whom will be a physician to answer any questions about cessation medications. The investigators will follow a script, using the seven steps recommended by the National Resource Center for Academic Detailing:[31] 1) The Introduction; 2) Needs Assessment; 3) Key Messages/Features/Benefits; 4) Understanding Barriers and Enablers; 5) Identifying and Handling Objections; 6) Summary; and 7) Close. The key message (Step 3) will include demonstration of the clinical reminder, review of the evidence for smoking cessation medications and how to prescribe them, and review of the role of the facility Health Promotion staff and how to contact them. Note that detailing will occur after randomization, so each psychiatrist will receive a detailing visit on the specific intervention to which he or she will be exposed.

6.1.1 Control Arm

Arm 1: OPT-IN Clinical Reminder

To increase actual and perceived behavior control and to increase perceived prioritization (disciplinary norms) of the treatment of psychiatric patients who smoke, we will implement a

CONFIDENTIAL

This material is the property of the NYU School of Medicine and NYU Langone Health. Do not disclose or use except as authorized in writing by the study sponsor

Behavioral Intervention Template Version: 11 January 2019

tobacco clinical reminder embedded within the EHR. Tobacco use clinical reminders are a best practice recommended by the PHS tobacco treatment guidelines and are routinely tested and used to address tobacco in primary care settings.[6] All VA facilities currently use clinical reminders, which are adapted locally and can be adapted for specific individuals or groups of providers. We will adapt the clinical reminder currently in use in Primary Care Clinics at VA New York Harbor Healthcare System, to make it suitable for the treatment of psychiatric patients who smoke. As we have done previously, the reminder will be self-explanatory, and will walk providers through each step of the 3A's approach. The reminder will include the following domains:

1. *Ask and Advise* – Providers will be prompted to ask their patients if they currently use tobacco and advise the patient to quit and to use treatment if interested in quitting.
2. *Assist: Medications* – Providers will be able to order cessation medications by clicking a box associated with an order template embedded in the reminder. The VA already has pre-set ordering templates for NRT (patch, gum, and lozenge), bupropion, and varenicline. For the proposed study, we will set combination NRT (patch plus gum or lozenge) as the preferred medication.
3. *Assist: Referral to Counseling* – Providers will be able to refer patients to the local cessation counseling program by clicking a consult box embedded in the reminder. The consult will be sent to the facility's Health Behavior Coordinator who runs the local cessation program. Program staff will proactively contact the patient to offer group behavioral counseling or warm-transfer to the VA Quitline via 3-way call for telephone counseling.
4. *Assist: Handout* – The provider will be able to print out a handout for patients with: a) The local phone number for the VA NY Harbor Healthcare System Health Behavior Coordinator, b) Instructions for smoking cessation medications, and c) Information about the VA Quitline and text messaging service.

Completing the reminder will turn it off for nine months. The reminder will be specific for psychiatrists – i.e., it will only be turned off if completed by a psychiatrist. The Tobacco Use Cessation clinical reminder that primary care providers complete will still be in effect and will be completely separate from this psychiatry reminder.

7.1.1 Study Specific Procedures

7.1.1.1 Psychiatrist training

One month before implementation of the provider training and reminders, all psychiatrists in the facility will be notified of the study at a required staff meeting.. [name] will deliver a psychiatrist training adapted from [name], tailored for training psychiatrists on tobacco use cessation for mental health patients.

7.1.1.2 Provider Randomization and Baseline Survey.

Psychiatrists will be approached and given the opportunity to choose to participate in the study or opt out of participating. At this time, psychiatrists will also have the option to ask questions. Completion of the baseline survey during this point will serve as study assent and psychiatrist will then be randomized into the control group or the intervention group.

7.1.1.3 Intervention (Clinical Reminders)

Participants will be given the intervention components outlined in section 6.1 above.

Psychiatrists who do not opt-out of participation will be randomized to one of the two study arms, stratified by their patient panel size and by the number of patients who smoke (captured as a health factor in the EHR) in their prior-year panel. Psychiatrists in the control arm will receive a clinical reminder similar to the one they currently receive as mandated by national standard. Psychiatrists in the intervention arm will receive a modified clinical reminder that is tailored for an opt-out smoking cessation approach.

7.1.1.4 Post-Visit Patient Survey

Patient PHI, including names, phone numbers, mental and physical health information, and tobacco-related measures will be obtained through CPRS and patients who see a participating psychiatrist. Once a month during the 6-month intervention period we will survey a random sample of patients seen by a participating psychiatrist within 24 hours of their visit. The survey

CONFIDENTIAL

will ask patients whether their psychiatrist asked them about their smoking, and offered NRT and counseling, as well as the patient's sociodemographics, smoking behavior, cessation treatment use, and motivation to quit.

7.1.1.5 Six Month Follow-up Psychiatrist Survey and Patient Survey

We will use a repeated measures design to conduct an email or paper survey with participating psychiatrists at baseline and 6 months assessing their attitudes, beliefs, motivations and intentions to treat tobacco. We will also assess patient use of cessation treatment and tobacco abstinence 6 months after seeing a participating psychiatrist in the two arms. For this aim, we will conduct a follow-up telephone survey with the 400 cluster-sampled patients who completed a post-visit survey during the intervention period

7.1.1.6 Follow-up Qualitative Interview with Psychiatrists

Guided by the Proctor and CFIR models, we will conduct semi-structured interviews with 12-14 psychiatrists (6-7 per arm) assessing their views on the appropriateness, acceptability and sustainability of the intervention components, as well as how the clinic's *inner setting* (e.g., culture, norms, workflow compatibility with the intervention), *outer setting* (e.g., VA policies, psychiatric professional associations), *psychiatrist characteristics* (e.g., beliefs about the intervention), and the *implementation process* (e.g., how providers were informed, who championed the intervention) may impact their views on appropriateness, acceptability and sustainability. We will also ask psychiatrists for their insights into challenges and successes encountered during their participation in the intervention components.

7.1.2 **Standard of Care Study Procedures**

Participants will receive their regular psychiatric care and tobacco treatment during the study. Study staff will not be involved in standard of care procedures.

8 **Assessment of Safety**

8.1.1 **Definition of Adverse Events (AE)**

An **adverse event** (AE) is any symptom, sign, illness or experience that develops or worsens in severity during the course of the study. Intercurrent illnesses or injuries should be regarded as adverse events. Abnormal results of diagnostic procedures are considered to be adverse events if the abnormality:

- results in study withdrawal
- is associated with a serious adverse event
- is associated with clinical signs or symptoms
- leads to additional treatment or to further diagnostic tests
- is considered by the investigator to be of clinical significance

8.1.2 **Definition of Serious Adverse Events (SAE)**

Serious Adverse Event

CONFIDENTIAL

Adverse events are classified as serious or non-serious. A **serious adverse event** is any AE that is:

- fatal
- life-threatening
- requires or prolongs hospital stay
- results in persistent or significant disability or incapacity
- a congenital anomaly or birth defect
- an important medical event

Important medical events are those that may not be immediately life threatening, but are clearly of major clinical significance. They may jeopardize the subject, and may require intervention to prevent one of the other serious outcomes noted above. For example, drug overdose or abuse, a seizure that did not result in in-patient hospitalization, or intensive treatment of bronchospasm in an emergency department would typically be considered serious.

All adverse events that do not meet any of the criteria for serious should be regarded as **non-serious adverse events**.

8.1.3 Definition of Unanticipated Problems (UP)

Unanticipated Problems Involving Risk to Subjects or Others

Any incident, experience, or outcome that meets all of the following criteria:

- Unexpected in nature, severity, or frequency (i.e. not described in study-related documents such as the IRB-approved protocol or consent form, the investigators brochure, etc)
- Related or possibly related to participation in the research (i.e. possibly related means there is a reasonable possibility that the incident experience, or outcome may have been caused by the procedures involved in the research)
- Suggests that the research places subjects or others at greater risk of harm (including physical, psychological, economic, or social harm).

8.2 Classification of an Adverse Event

8.2.1 Severity of Event

For AEs not included in the protocol defined grading system, the following guidelines will be used to describe severity.

- **Mild** – Events require minimal or no treatment and do not interfere with the participant's daily activities.
- **Moderate** – Events result in a low level of inconvenience or concern with the therapeutic measures. Moderate events may cause some interference with functioning.
- **Severe** – Events interrupt a participant's usual daily activity and may require systemic drug therapy or other treatment. Severe events are usually potentially life-threatening or incapacitating.

CONFIDENTIAL

8.2.2 Relationship to Study Intervention

The clinician's assessment of an AE's relationship to study intervention is part of the documentation process, but it is not a factor in determining what is or is not reported in the study. If there is any doubt as to whether a clinical observation is an AE, the event should be reported. All AEs must have their relationship to study intervention assessed. In a clinical trial, the study intervention must always be suspect. To help assess, the following guidelines are used.

- **Related** – *The AE is known to occur with the study intervention, there is a reasonable possibility that the study intervention caused the AE, or there is a temporal relationship between the study intervention and event. Reasonable possibility means that there is evidence to suggest a causal relationship between the study intervention and the AE.*
- **Not Related** – *There is not a reasonable possibility that the administration of the study intervention caused the event, there is no temporal relationship between the study intervention and event onset, or an alternate etiology has been established.*

8.2.3 Expectedness

The PI will be responsible for determining whether an AE is expected or unexpected. An AE will be considered unexpected if the nature, severity, or frequency of the event is not consistent with the risk information previously described for the study intervention.

8.3 Time Period and Frequency for Event Assessment

AEs and SAEs can be identified during any study procedure. When a study staff member learns of an AE or SAE, he or she will report it to the PI with 24 hours. All AEs, SAEs and Ups will be documented using standardized forms created for the study.

8.4 Reporting Procedures – Notifying the IRB

AEs, SAEs, and UPs will be reported to the IRB based on NYU SoM IRB reporting guidelines. The report will include:

- Protocol identifying information: protocol title and number, PI's name, and the IRB project number;
- A detailed description of the event, incident, experience, or outcome;
- An explanation of the basis for determining that the event, incident, experience, or outcome represents an AE, SAE or UP;
- A description of any changes to the protocol or other corrective actions that have been taken or are proposed in response to the AE, SAE or UP.

The PI will complete and sign all reports.

9 Statistical Considerations

9.1 Statistical Hypotheses

We hypothesize that an opt-out approach will be more effective at increasing tobacco screenings, NRT prescriptions and referrals to cessation counseling.

CONFIDENTIAL

9.2 Description of Statistical Methods

9.2.1 General Approach

We will first summarize survey and administrative data using descriptive statistics (means, medians, standard deviations, frequency distributions, and graphical displays) to characterize providers and patients treated by the providers in the two intervention arms.

9.2.2 Analysis of the Primary Efficacy Endpoint(s)

AIM 1: Estimate the effects of an Opt-Out versus Opt-In Tobacco Treatment System on the proportion of mental health patients who are screened and treated for tobacco use by their psychiatrist.

Based on administrative data, we will categorize the proportion of patients seen by a participating psychiatrist in each group who were: (1) screened for tobacco use by the psychiatrist, (2) among smokers, received a cessation medication prescription from the psychiatrist, and (3) among smokers, referred to cessation counseling by the psychiatrist. We will use generalized linear mixed effect models (GLMMs) to compare these screening and treatment rates between groups. For all analyses, sensitivity analyses will be used to evaluate the impact on results from missing data and subject dropout. Specifically, missingness will be handled by creating a separate category, or removed by multiple imputation (MI). An intent-to-treat (ITT) approach will be compared with a complete-case only method.

AIM 2: Assess intervention fidelity, provider perceptions, and barriers and facilitators to implementation: For intervention fidelity, we will use descriptive statistics to summarize the patient post-visit survey data to calculate the proportion of patients seen by a participating psychiatrist in each study arm who were asked about smoking, offered medications, offered counseling referral, and (among those offered) the proportion of patients who accepted medications and referral. We will also summarize training fidelity logs (the proportion of psychiatrists who attended the trainings and received an academic detailing session). To assess provider perceptions quantitatively, we will summarize provider survey data using descriptive statistics (means, standard deviations) to understand providers' attitudes and beliefs regarding treating their patients for tobacco. For our qualitative data analysis (interviews, observations, reflection memos, meeting minutes), we will use a three-step coding process for each data source. First, two investigators will individually read a sub-sample of data (e.g., 3 interviews) to identify preliminary inductive codes, then meet to achieve consensus on coding the sub-sample and create the first draft of a code book. Second, the investigators will individually apply the codebook to a second sub-sample of data, and meet to achieve coding consensus on the second sub-sample to create final codebook for the data source. Third, once all data are coded, the investigators will meet to complete more focused coding to identify code clusters, relationships among codes, and common themes. Once all data sources are coded, we will also use group consensus meetings to look for themes across the four main data sources.

AIM 3: Estimate the effect of the Opt-Out Reminder versus the Opt-In Reminder on the use of cessation treatment and self-reported abstinence among mental health patients who smoke: We will use a similar analytic approach as in Aim 1. We will first categorize each patient as: (1) having achieved or not achieved 7-day abstinence 6 months after their psychiatry visit and (2) having used or not use any type of cessation treatment in the 6 months after their visit. This will estimate use of treatment and abstinence rates for each study arm. We will use GLMMs to compare these two outcomes between groups. Sensitivity analyses will be used to evaluate the impact on results

CONFIDENTIAL

This material is the property of the NYU School of Medicine and NYU Langone Health. Do not disclose or use except as authorized in writing by the study sponsor

from missing data and subject dropout. An IIT approach will be compared with the complete-case only method, but our primary analysis will be the complete case analysis, as The North American Quitline Consortium has found this approach to be more accurate in representing true quit rates and recommends use of this calculation,⁵² as do other reviews.⁵³

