4.1 Description of Study Design

This study will use a scientifically robust, mixed-methods, two-arm cluster-randomized study design. Study subjects are not NYULH employees or patients. We will implement a tobacco use clinical reminder for outpatient psychiatrists practicing at the VA New York Harbor Healthcare System (N = 20). Half of the psychiatrists will receive a reminder that encourages the psychiatrist to offer cessation medications and referral to cessation counseling to patients interested in quitting (Opt-In Reminder). The other half will receive a clinical reminder that includes a standing NRT order and a referral to cessation counseling that will automatically generate unless the provider actively opts-out (Opt-Out Reminder). Prior to implementation of the reminders, psychiatrists in both arms will receive a one-hour training on tobacco treatment and individual education outreach to demonstrate the clinical reminder and answer questions (academic detailing).

[figure not shown]
We will use VA administrative data extracted on all patient visits with a participating psychiatrist 6 months before and after implementation to calculate the study's primary outcomes: 1) the percent of patients screened for smoking, 2) the percent of smokers prescribed a cessation medication and 2) the percent of smokers referred to counseling. To assess intervention fidelity, we will use training logs to track psychiatrist attendance at group and academic detailing trainings. Over the intervention period, we will also conduct post-visit surveys with a cluster sample of 400 patients (20 per psychiatrist) to assess psychiatrist fidelity to the 3 A's approach. At the end of the intervention period, we will conduct semi-structured interviews with 12-14 psychiatrists (6-7/arm) asking about their perceptions of the intervention components. We will also analyze implementation observations (e.g., training observations, reflection memos) and documents (e.g., meeting minutes) for implementation barriers and facilitators. At six months, we will survey the clustered 400-patient sample again to evaluate the study's secondary outcomes: 1) patient use of cessation treatment in the prior 6 months and 2) self-reported 7-day abstinence at 6 months.

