One month before implementation of the provider training and reminders, all psychiatrists in the facility will be notified of the study at a required staff meeting. Psychiatrists will have the option at the meeting to ask questions and have the opportunity to opt-out of study participation. Psychiatrists will also have the opportunity to ask questions one-on-one with [name] before deciding whether to participate. Psychiatrist turn-over is low at the facility; however, during recruitment we will ask psychiatrists if they plan to leave in the next 6 months and only enroll those who have no plans to leave. When [name] used this approach to provider participation in a study implementing a new tobacco treatment model in VA NYHHS primary care clinics, 50 of 51 primary care providers participated.[24] In the ongoing CHORD study, led by [name], no primary care providers opted out of participation. We conservatively anticipate that 20 of 24 psychiatrists at the VA NYHHS will participate.

CONFIDENTIAL

Psychiatrists who do not opt-out of participation will be randomized to one of the two study arms, stratified by their patient panel size and by the number of patients who smoke (captured as a health factor in the EHR) in their prior-year panel. Randomization will be supervised by the study's statistician. Psychiatrists who opt-out of study participation will receive the opt-in clinical reminder as a part of their routine care, but their performance will not be included in study analyses.

Figure 1. Overview of study design

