9.3 Sample Size

We aim to enroll all practicing psychiatrists at the VA New York Harbor Healthcare System, but have conservatively estimated that 20 will enroll. This sample will allow us to study provider behavior during approximately 4,000 unique patient visits over 6 months. We calculated the level of power this will provide us to find a significant group effect on the proportion of patients prescribed a cessation medication by their psychiatrist (primary outcome 2). Our power calculation varied the intraclass correlation (ICC) of 0.05-0.15 based on a cluster-randomized trial of preventive care in primary care practices.⁵⁴ We estimate that 10% of patients in Arm 1 will receive a prescription.¹⁵ With the smallest ICC of 0.05, a type I error of 5%, and 80% power, 4,000 visits will provide us with enough power to detect a 21% or greater prescription rate in Arm 2. With the largest ICC of 0.15, a type I error of 5%, and 80% power, 4,000 visits will provide us with enough power to detect a 29% or greater prescription rate in Arm 2.

10 Ethics/Protection of Human Subjects

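### Randomisation is stratified by panel size and smoker count, but the Aim 1 and Aim 3 GLMMs do not say whether the strata are in the model; if the strata are prognostic, omitting them forgoes precision with about 20 clusters

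*Combined protocol and SAP*

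**What the plan says.** Section 4.1 states that participating psychiatrists are "randomized to one of the two study arms, stratified by their patient panel size and by the number of patients who smoke". Section 7.1.1.3 repeats this: "stratified by their patient panel size and by the number of patients who smoke". The smoker count comes from the prior-year panel. Neither section gives cut-points or the number of strata.

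For Aim 1, section 9.2.2 says: "We will use generalized linear mixed effect models (GLMMs) to compare these screening and treatment rates between groups". For Aim 3 it says "We will use a similar analytic approach as in Aim 1" and "We will use GLMMs to compare these two outcomes between groups". The Protocol Summary describes both analyses in the same terms. No fixed effects beyond the group comparison, no random-effect structure and no degrees-of-freedom method are named. Section 9.2.1 is purely descriptive.

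On size, section 9.3 says the investigators "have conservatively estimated that 20 will enroll", and adds: "This sample will allow us to study provider behavior during approximately 4,000 unique patient visits over 6 months". The power calculation there uses an ICC of 0.05 to 0.15 and does not mention stratification.

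**The concern.** Stratified allocation balances the arms on the strata, so differences between strata largely drop out of the true variance of the arm contrast. A model without the strata leaves those differences in the estimated psychiatrist variance. If the strata predict the outcome, the reported standard error is then larger than the true one, intervals over-cover, and the test rejects less often than its nominal level.

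This matters more than usual here because precision is set by about 20 psychiatrists, not by the number of visits. It also matters that the choice is open. With 20 clusters and three primary outcomes, deciding on adjustment after seeing the data could move a p-value.

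**Working it through.** **Inputs from the plan.** 20 psychiatrists (9.3), half per arm (4.1), hence 10 per arm. About 4,000 visits (9.3), hence 4,000/20 = 200 per psychiatrist and 2,000 per arm. Arm 1 rate 10%, ICC 0.05 to 0.15, type I error 5%, power 80% (9.3). Two-sided testing is assumed, because the plan does not state sidedness.

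**The plan's own figures first.** The design effect is 1 + (200 - 1) x ICC.
- ICC 0.05: 1 + 199 x 0.05 = 10.95; effective n per arm 2,000/10.95 = 182.6.
- ICC 0.15: 1 + 199 x 0.15 = 30.85; effective n per arm 2,000/30.85 = 64.8.

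The detectable rate p2 solves p2 - 0.10 = (1.96 + 0.842) x sqrt[(0.10 x 0.90 + p2(1 - p2))/n_eff]. This gives 20.4% and 28.9%, which round up to the stated 21% and 29%. The figures reproduce with no stratification term. At the stated rates a t-test on 18 df has 79.4% and 75.8% power, so there is little slack.

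**How much the standard error is overstated.** On a scale where the patient-level variance is 1, a psychiatrist's mean has variance ICC + (1 - ICC)/m. If the strata explain a share R2 of the between-psychiatrist part, the variance that matters after stratified allocation is ICC(1 - R2) + (1 - ICC)/m. The approximate inflation is the square root of the ratio. For m = 200 and R2 = 0.3:
- ICC 0.05: sqrt(0.05475/0.03975) = 1.17.
- ICC 0.15: sqrt(0.15425/0.10925) = 1.19.

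For Aim 3, with the planned 20 patients per psychiatrist and, by assumption, the same ICCs, it is smaller: sqrt(0.0975/0.0825) = 1.09 and sqrt(0.1925/0.1475) = 1.14.

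**Simulation at the plan's rates and ICCs.** R2 is an assumption, ranged from 0 to 0.5. There were 8,000 runs per cell, with four strata of 6, 4, 4 and 6 psychiatrists, 1:1 allocation within strata, and a psychiatrist-level analysis on the risk-difference scale. Without strata the test has 18 df; with two binary factors it has 16.

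| ICC | R2 | Power without strata | Power with strata | Type I error without | Type I error with |
|---|---|---|---|---|---|
| 0.05 | 0 | 80.3% | 79.8% | 5.3% | 5.3% |
| 0.05 | 0.1 | 79.6% | 82.0% | 4.1% | 5.3% |
| 0.05 | 0.3 | 82.5% | 90.5% | 2.3% | 4.9% |
| 0.05 | 0.5 | 84.8% | 96.2% | 0.9% | 5.2% |
| 0.15 | 0 | 75.3% | 74.9% | 5.6% | 5.5% |
| 0.15 | 0.1 | 76.9% | 79.5% | 4.2% | 5.4% |
| 0.15 | 0.3 | 78.8% | 88.1% | 2.0% | 4.9% |
| 0.15 | 0.5 | 81.2% | 95.4% | 0.6% | 4.9% |

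At ICC 0.05, the mean unadjusted standard error divided by the empirical SD is 1.00, 1.04, 1.19 and 1.39 across the four R2 values.

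**A less favourable set-up.** Here two underlying factors with correlation 0.8 are split at the median, allocation is only near-balanced within the four strata, and the effect is 1.325 SD. At R2 = 0, 0.1, 0.2, 0.3 and 0.4, power is 80, 82, 85, 86 and 88% without the strata and 77, 81, 86, 91 and 94% with them. Type I error is 4.5, 3.5, 2.9, 2.3 and 1.5% without them and 4.6 to 5.3% with them.

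Taking both set-ups, adjustment changes power by about -0.5 to -3 points at R2 = 0, -1 to +2.5 at 0.1, and +5 to +9 at 0.3.

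**Dependence on the reference distribution.** The second set-up was rerun (12,000 runs) with maximum-likelihood variance and a z reference. Type I error without the strata was 7.6, 6.8, 5.0, 4.2 and 2.7% at R2 = 0 to 0.4; with both factors it was 9.3 to 10.2% throughout. A direct check agrees. The maximum-likelihood variance divides by 20 instead of the residual df, so the z cut-off of 1.96 corresponds to a t cut-off of 1.96/sqrt(20/16) = 1.753 on 16 df (two-sided tail 9.9%). Without the strata at R2 = 0 it is 1.96/sqrt(20/18) = 1.859 on 18 df (7.9%).

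**The case against.** The strongest reply is that section 9.2.2 is silent on all model terms, so a reader who infers that the GLMMs deliberately ignore the strata goes beyond the text. That stands: what can be said is that the plan does not specify them.

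Nor do the documents show that the strata are prognostic. The outcomes are percentages and the strata are counts, and nothing in the plan says that a larger panel or more smokers raises or lowers the prescribing percentage. The strata may have been chosen to balance denominators. That also stands. In the less favourable set-up, adjustment loses or roughly ties up to R2 = 0.2.

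A reader might also infer that the planned power is eroded. It is not: the 21% and 29% were derived without stratification, and unadjusted power tends to rise with R2 in both set-ups. Only a possible extra gain is forgone.

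Finally, conservatism is not guaranteed. With z-based inference the unadjusted test is anti-conservative at low R2, and adding the strata makes it worse. This objection does not remove the point, but it changes the remedy.

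What survives is that the factors used to randomise are not carried into the described analysis. Under t-based inference, including them keeps type I error near 5% at every R2 examined, at a small and bounded cost.

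**Conclusion.** The point holds as a gap in specification with a conditional loss of efficiency. If the strata predict the outcome and inference is t-based, fitting the GLMM with the arm term alone overstates the standard error by about 4-5% at R2 = 0.1 and 17-19% at R2 = 0.3. Power forgone at R2 = 0.3 is about 5 to 9 points. At R2 = 0 nothing is lost, and adjustment costs about 0.5 to 3 points.

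These sizes rest on an assumed R2, on equal clusters of 200, and on psychiatrist-level linear analyses standing in for the GLMM. In a logit GLMM, adjustment also changes the conditional odds ratio, so standard errors are not directly comparable on that scale. The 200 follows section 9.3 in counting all visits. Outcomes restricted to smokers have smaller clusters, which reduces the inflation, as the Aim 3 figures show. The change is worth making because it is cheap, uses data already held, and settles the choice in advance.

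**What to change.** Add to section 9.2.2, for example: *All Aim 1 and Aim 3 GLMMs include the randomisation factors (panel-size category and smoker-count category, as used for randomisation) as psychiatrist-level fixed effects. If the two categories nearly coincide, a single combined stratum term is used. Inference on the arm effect uses a small-sample degrees-of-freedom method (such as Kenward-Roger, or between-within degrees of freedom with a t reference), not Wald z.*

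State the cut-points and number of strata alongside the randomisation description, so that the model terms are defined before outcome data are seen. The two parts belong together, since adding the factors under Wald z would make false positives more likely.

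The cost is a short addition to the text and 1-2 of the 18 psychiatrist-level degrees of freedom, worth about 0.5 to 3 points of power if the factors predict nothing. No new data are needed.
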